3.3 Inclusion of Women and Minorities

Patients are eligible for this trial regardless of sex/gender, race, or ethnicity. Subject selection is equitable if they meet the inclusion and exclusion criteria. In conformance with the National Institutes of Health (NIH) Revitalization Act of 1993 (amended in October, 2001) with regard to inclusion of women and minorities in clinical research, possible interaction between race/ethnicity and treatment have been considered.

4. REGISTRATION PROCEDURES

4.1 Investigator and Research Associate Registration with CTEP

4.1.1 Investigator and Research Associate Registration with CTEP

Food and Drug Administration (FDA) regulations and National Cancer Institute (NCI) policy require all individuals contributing to NCI-sponsored trials to register and to renew their registration annually. To register, all individuals must obtain a Cancer Therapy Evaluation Program (CTEP) Identity and Access Management (IAM) account (<https://ctepcore.nci.nih.gov/iam>). In addition, persons with a registration type of Investigator (IVR), Non-Physician Investigator (NPIVR), or Associate Plus (AP) (i.e., clinical site staff requiring write access to OPEN or RAVE or acting as a primary site contact) must complete their annual registration using CTEP's web-based Registration and Credential Repository (RCR) (<https://ctepcore.nci.nih.gov/rcr>). Documentation requirements per registration type are outlined in the table below.

Documentation Required	IVR	NPIVR	AP	A
FDA Form 1572	✓	✓		
Financial Disclosure Form	✓	✓	✓	
NCI Biosketch (education, training, employment, license, and certification)	✓	✓	✓	
HSP/GCP training	✓	✓	✓	
Agent Shipment Form (if applicable)	✓			
CV (optional)	✓	✓	✓	

An active CTEP-IAM user account and appropriate RCR registration is required to access all CTEP and CTSU (Cancer Trials Support Unit) websites and applications. In addition, IVRs and NPIVRs must list all clinical practice sites and IRBs covering their practice sites on the FDA Form 1572 in RCR to allow the following:

- Added to a site roster
- Assigned the treating, credit, consenting, or drug shipment (IVR only) tasks in OPEN
- Act as the site-protocol PI on the IRB approval
- Assigned the Clinical Investigator (CI) role on the Delegation of Tasks Log (DTL).

For questions, please contact the RCR **Help Desk** by email at <[contact]>.

Additional information can be found on the CTEP website at

<https://ctep.cancer.gov/investigatorResources/default.htm>.

4.2 Site Registration

This study is supported by the NCI Cancer Trials Support Unit (CTSU).

Each investigator or group of investigators at a clinical site must obtain IRB approval for this protocol and submit IRB approval and supporting documentation to the CTSU Regulatory Office before they can be approved to enroll patients. Assignment of site registration status in the CTSU Regulatory Support System (RSS) uses extensive data to make a determination of whether a site has fulfilled all regulatory criteria including but not limited to the following:

- An active Federal Wide Assurance (FWA) number
- An active roster affiliation with the Lead Network or a participating organization

A valid IRB approval

- Compliance with all protocol specific requirements

In addition, the site-protocol Principal Investigator (PI) must meet the following criteria:

- Active registration status
- The IRB number of the site IRB of record listed on their Form FDA 1572
- An active status on a participating roster at the registering site

Sites participating on the NCI CIRB initiative that are approved by the CIRB are not required to submit separate IRB approval documentation to the CTSU Regulatory Office. For sites using the CIRB, IRB approval information is received from the CIRB and applied to the RSS in an automated process. Signatory institutions must submit a Study Specific Worksheet for Local Context (SSW) to the CIRB (via IRBManager) to indicate their intention to open the study locally. The CIRB's approval of the SSW is then communicated to the CTSU Regulatory Office. In order for the SSW approval to be processed, the Signatory Institution must inform the CTSU which CIRB-approved institutions aligned with the Signatory Institution are participating in the study.

4.2.1 Downloading Regulatory Documents

Site registration forms may be downloaded from the 9979 protocol page located on the CTSU Web site. Permission to view and download this protocol is restricted and is based on person and site roster data housed in the CTSU RSS. To participate, Investigators and Associates must be associated with the Corresponding or Participating protocol organization in the RSS.

- Go to <https://www.ctsu.org> and log in using your CTEP IAM username and password.
- Click on the Protocols tab in the upper left of your screen.
- Either enter the protocol # in the search field at the top of the protocol tree or Click on the By Lead Organization folder to expand, then select LAO-MN026 and protocol # 9979.
- Click on LPO Documents, select the Site Registration documents link, and download and complete the forms provided. (Note: For sites under the CIRB

initiative, IRB data will load to RSS as described above.)

4.2.2 Submitting Regulatory Documents

Requirements For 9979 Site Registration

- IRB approval (For sites not participating via the NCI CIRB; local IRB documentation, an IRB-signed CTSU IRB Certification Form, Protocol of Human Subjects Assurance Identification/IRB Certification/Declaration of Exemption Form, or combination is accepted)
- Credentialing for performing neurocognitive testing through existing mechanisms within cooperative groups including but not limited to participation in a prior NRG or Alliance or any other cooperative group study or other PI approved measures including but not limited to credentialing through training arranged by the stud PI (or representative) or participating site's internal training. Each participating site should review the credentialing process with the study PI (or representative) prior to site activation.
- Completion of a Site Initiation Visit teleconference (SIV TC) with the lead site

4.2.4 Checking Site Registration Status

You can verify your site registration status on the members' section of the CTSU Web site.

- Go to <https://www.ctsu.org> and log in using your CTEP IAM username and password.
- Click on the Regulatory tab at the top of your screen.
- Click on the Site Registration subtab.
- Enter your 5-character CTEP Institution Code and click on Go.

Note: The status given only reflects compliance with IRB documentation and institutional compliance with protocol-specific requirements as outlined by the Lead Network. It does

not reflect compliance with protocol requirements for individuals participating on the protocol or the enrolling investigator's status with the NCI or their affiliated networks.

4.3 Patient Registration

4.3.1 OPEN / IWRS

Patient enrollment will be facilitated using the Oncology Patient Enrollment Network (OPEN). OPEN is a web-based registration system available to users on a 24/7 basis. It is integrated with the CTSU Enterprise System for regulatory and roster data interchange and with the Theradex Interactive Web Response System (IWRS) for retrieval of patient registration/randomization assignment. Patient enrollment data entered by Registrars in OPEN / IWRS will automatically transfer to the NCI's clinical data management system, Medidata Rave.

For trials with slot reservation requirements, OPEN will connect to IWRS at enrollment initiation to check slot availability. Registration staff should ensure that a slot is available and secured for the patient before completing an enrollment.

The OPEN system will provide the site with a printable confirmation of registration and treatment information. Please print this confirmation for your records.

4.3.2 OPEN/IWRS User Requirements

OPEN/IWRS users must meet the following requirements:

- Have a valid CTEP-IAM account (*i.e.*, CTEP username and password).
- To enroll patients or request slot reservations: Be on an ETCTN Corresponding or Participating Organization roster with the role of Registrar. Registrars must hold a minimum of an AP registration type.
- To approve slot reservations or access cohort management: Be identified to Theradex as the "Client Admin" for the study.
- Have regulatory approval for the conduct of the study at their site.

Prior to accessing OPEN/IWRS, site staff should verify the following:

- All eligibility criteria have been met within the protocol stated timeframes.
- If applicable, all patients have signed an appropriate consent form and HIPAA authorization form.

4.4 General Guidelines

Following registration, patients should begin protocol treatment as rapidly as possible. Issues that would cause treatment delays should be discussed with the Principal Investigator. If a patient does not receive protocol therapy following registration, the patient's registration on the study may be canceled. The Study Coordinator should be notified of cancellations as soon as possible.

5. TREATMENT PLAN

5.1 Agent Administration

Treatment will be administered on an outpatient basis. Reported adverse events and potential risks are described in Section 7. Appropriate dose modifications are described in Section 6. No investigational or commercial agents or therapies other than those described below may be administered with the intent to treat the patient's malignancy. 5-iodo-2-pyrimidinone-2'-deoxyribose (IPdR) (NSC 726188) will be delivered by oral (po) administration in capsule form once daily x 28 days. The capsules will be taken on an empty stomach (either 1 hour before or 2 hours after meals).

IPdR will be administered alone without WBRT during Week 1 (7 calendar days) and with WBRT during Weeks 2-4. On days when IPdR and WBRT are given concurrently, IPdR should be administered within 30 minutes to 2 hours prior to WBRT.

Because IPdR is an orally administered agent patients will be requested to maintain a medication diary of each dose of medication. The medication diary will be returned to clinic staff at the end of each course.

Since the IPdR half-life is <1 day, 5 half-lives will be less than 1 week. Hence, an observation period up to D35 (D1 being 1st day of IPdR) is required to assess toxicity before enrolling a patient at the next IPdR dose level. Patients will be allowed to initiate systemic therapy per clinician preference after the D35 assessment.

The starting dose for IPdR for Phase 1 testing is based on the most sensitive (lower MTD) of the two animal species tested, *i.e.* ferrets and rats [44, 45]. The MTD for IPdR in ferrets, the most sensitive species, was determined to be ≤ 150 mg/kg/d for 14 days[45], which is equivalent to 850 mg/M²/day for 14 days. The human equivalent dose (HED) is also 850 mg/M²/day, the same as the ferret dose, based on body surface area (BSA).[48] Based on these calculations and pre-clinical animal data, 1/10th of the MTD is 85 mg/M²/day (150 mg), the starting dose for this trial.

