1.3 Correlative Objectives (in 6 additional patients accrued at RP2D)

1.3.1 To assess for biochemical evidence of IPdR effect in normal tissues (circulating granulocytes) by measuring %IUDR-DNA cellular incorporation by flow cytometry and high-pressure liquid chromatography (HPLC) analyses as an exploratory biomarker for the following effects:

- The %IUDR-DNA tumor cell incorporation from Day 8 extracranial tumor biopsies in brain metastasis cancer patients receiving RP2D doses of IPdR as an exploratory biomarker of tumor radiosensitization using RECIST criteria.
- The %IUDR-DNA cellular incorporation in patients' circulating granulocytes taken weekly during the 28-day IPdR RP2D dose, on Day 29, and Week 8 as an exploratory biomarker of IPdR systemic toxicities to bone marrow as measured by serial CBC/differential values

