Correlation will be performed of the %IUdR-DNA cellular incorporation in peripheral (circulating) granulocytes as an exploratory biomarker of bone marrow acute normal tissue toxicity with the po IPdR RP2D and RP2D pharmacokinetics. This exploratory assay was originally developed in [name] laboratory at NCI.[55] Additionally, we do not expect a linear relationship between the %IUdR-DNA cellular incorporation in circulating granulocytes and peripheral blood counts measured weekly during RP2D drug exposures and at Day 29 and Week 8 follow-up. Nevertheless, we will test the hypothesis that IPdR drug dose and drug plasma pharmacokinetics will be linearly related to the %IUdR-DNA cellular incorporation in circulating granulocytes.

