- e. On Days 15 and 22 of the 28-day dosing schedule, blood will be obtained just prior to the po drug administration and then at 30, 60, 120 and 240 minutes following po dosing. A five minute positive or negative margin on each of the above times on Day 1 (30 through 240 minutes) is acceptable.
- f. %IUDR-DNA cellular incorporation. Sample collection will be prior to study (Day 1) and at Days 8, 15, 22 and 29 of the 28-day treatment followed by first two-month follow up.
- g. Follow-up MRI at 6 months (\pm 2 week) from the completion of WBRT is required. As guided by institutional practices, MRIs are also recommended during follow-up visits every 2 months (\pm 1 week) for the first 6 months and every 3-4 months (\pm 2 weeks) for the next 6 months from the completion of WBRT. If progressive disease is seen on MRI, subsequent evaluations are not required for study.
- h. For patients accrued to part 2 of the study, please send anonymized pre- and post-treatment (up to 6 months from the date of completion of WBRT) scans via FTP or hard copy CD to the study PI for central review of response.
- i. From the date of completion of WBRT, follow-up visits to be done every 2 months (\pm 1 week) for the first 6 months, then and are recommended every 3-4 months (\pm 2 weeks) for the next 6 months then every 6 months (\pm 3 weeks) for the next one year. These visits can be performed at an outside institution if appropriate research staff (credentialed and registered as a study team member prior to the evaluations) is available to complete adverse event, neurocognitive testing and QOL evaluation. After the first 6 months of follow up, clinic visits may be replaced by phone calls or visits at an outside institution. Follow up notes or documentation of phone calls must be included in the study chart.
- j. Neurocognitive and quality of life evaluation to be performed at the D35 assessment time-point and then during follow-up visits every 2 months (\pm 1 week) for the first 6 months from the date of completion of WBRT (for patients without intracranial progression). A total of 5 neurocognitive and quality of life evaluations will be performed: Baseline, D35, 2-, 4- and 6- months from the date of completion of WBRT.
- k. To be performed only if feasible if the patient is removed from the study.
- l. Perform biopsy only if patient has an easily accessible tumor.
- R. Research.

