13.4 Analysis of Secondary Endpoints

13.4.1 Tumor Response

Best Response is defined to be the best objective status recorded from the start of the treatment until disease progression/recurrence. The patient's best response assignment will depend on the achievement of measurement criteria as described in section 11.0. Responses will be summarized by simple descriptive summary statistics delineating complete and partial responses as well as stable and progressive disease in this patient population (overall and by tumor group). The number of responses may indicate further evaluation for specific tumor types in a Phase 2 setting. Only patients in Part 2 of the study will be included in this evaluation.

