13.4.4 Intracranial progression free survival (icPFS) and Overall Survival (OS)

These will be explored using the Kaplan-Meier method. For estimation of icPFS, patients alive without intracranial progression at last follow-up will be censored at the date of the last radiologic assessment whereas intracranial progression or death will be scored as events. The icPFS estimates at 6 months with their standard error of the estimate will be reported. For calculation of OS, patients alive at last follow-up will be censored.

13.4.5 Incidence of delayed neurological toxicity at 2, 4 and 6-months (\pm 1 week) post-completion of WBRT (for patients without intracranial progression) including:

- a. Delayed-recall through HVLT-R**
- b. Quality of life as measured by the FACT-BR**

REFERENCES

1. Posner, J.B. and N.L. Chernik, Intracranial metastases from systemic cancer. *Adv Neurol*, 1978. 19: p. 579-92.
2. Stewart, B.W., P. Kleihues, and I.A.f.R.o. Cancer, *World cancer report*. Vol. 57. 2003: IARC press Lyon.
3. Gaspar, L.E., et al., Validation of the RTOG recursive partitioning analysis (RPA) classification for brain metastases. *Int J Radiat Oncol Biol Phys*, 2000. 47(4): p. 1001-6.
4. Nussbaum, E.S., et al., Brain metastases. Histology, multiplicity, surgery, and survival. *Cancer*, 1996. 78(8): p. 1781-8.
5. Sperduto, P.W., et al., Summary report on the graded prognostic assessment: an accurate and facile diagnosis-specific tool to estimate survival for patients with brain metastases. *J Clin Oncol*, 2012. 30(4): p. 419-25.
6. Tsao, M.N., et al., Whole brain radiotherapy for the treatment of newly diagnosed multiple brain metastases. *Cochrane Database Syst Rev*, 2012. 4: p. CD003869.
7. Young, D.F., et al., Rapid-course radiation therapy of cerebral metastases: results and complications. *Cancer*, 1974. 34(4): p. 1069-76.
8. Rades, D., et al., Dose escalation beyond 30 grays in 10 fractions for patients with multiple brain metastases. *Cancer*, 2007. 110(6): p. 1345-50.
9. Chao, J.H., R. Phillips, and J.J. Nickson, Roentgen-ray therapy of cerebral metastases. *Cancer*, 1954. 7(4): p. 682-9.
10. Gaspar, L.E., et al., The role of whole brain radiation therapy in the management of newly diagnosed brain metastases: a systematic review and evidence-based clinical practice guideline. *J Neurooncol*, 2010. 96(1): p. 17-32.

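### Anticancer therapy may start once the D35 assessment is done, before any scheduled follow-up MRI, yet best response and intracranial PFS are analysed without regard to it

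*Combined protocol and SAP*

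**What the plan says.** **Later therapy.** Section 5.1: "Patients will be allowed to initiate systemic therapy per clinician preference after the D35 assessment". Sections 3.2.3 (exclusion criteria) and 5.1.4.2 (technical factors) add radiosurgery, fractionated boosts and neurosurgery once DLT assessment has been completed.

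**Response.** Section 13.4.1: "Best Response is defined to be the best objective status recorded from the start of the treatment until disease progression/recurrence". It reports responses overall and by tumour group, and says their number may point to tumour types for phase 2 study. Objective 1.2.1 presents the reading as anti-tumour activity of IPdR-mediated radiosensitization.

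**Intracranial PFS.** Section 13.4.4 uses Kaplan-Meier with intracranial progression or death as events; "patients alive without intracranial progression at last follow-up will be censored at the date of the last radiologic assessment". New therapy is not mentioned there, nor in 11.1.4.3, 11.1.5 or 11.1.6.

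**Marrow marker.** Objective 1.3.1 has granulocyte samples "taken weekly during the 28-day IPdR RP2D dose, on Day 29, and Week 8 as an exploratory biomarker of IPdR systemic toxicities to bone marrow". Section 2.6.3 refers to "peripheral blood counts measured weekly during RP2D drug exposures and at Day 29 and Week 8 follow-up". Calendar footnote f instead lists Days 1, 8, 15, 22 and 29 "of the 28-day treatment followed by first two-month follow up", as does 9.2.2.

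**What the plan does with later therapy.** Sections 5.1.3 and 5.2 take it into account for the late-toxicity decision only. Section 5.3 requires the case report form to capture concurrent drugs, but no analysis uses that information.

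**The concern.** In a single-arm study, a response or PFS figure can be read as activity of IPdR plus WBRT only if the reader knows what else the patient had received by then. Here a drug of the clinician's choice, or a procedure aimed at the measured brain lesions, may start before the first scheduled follow-up scan. A resulting shrinkage or delay in progression is counted like any other.

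The reading most exposed is the tumour-group breakdown in 13.4.1. Tumour types with intracranially active systemic drugs would tend to look best for reasons unrelated to radiosensitization, and that breakdown is what may steer phase 2. Section 2.6.2 also takes tumour response as the dependent variable against Day 8 %IUdR-DNA, so the same problem enters that correlation.

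The plan attends to such problems elsewhere. Section 11 leaves Part 1 patients out of response to reduce heterogeneity, and 5.3 discusses memantine as a complication for the neurocognitive results. Later anticancer therapy gets no such treatment for response or PFS.

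**Working it through.** There is no figure in the plan to reproduce here. The check is schedule arithmetic, then an illustration.

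**Inputs.** D1 is the first IPdR dose (5.1). The last WBRT fraction is D26 (schema). The DLT visit is D35 or up to 3 days later (calendar). Scan times come from 5.5 and calendar footnote g, PFS assessment times from 11.1.6. One month is 30.44 days. The table takes a patient who starts new therapy at D36-D38.

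| Reading | Study day | Days on new therapy |
|---|---|---|
| First recommended MRI, 2 months ± 1 week after WBRT | 26 + 61 ± 7 = D80-D94 | 80 − 38 = 42 to 94 − 36 = 58 |
| Required MRI, 6 months ± 2 weeks after WBRT | 26 + 183 ± 14 = D195-D223 | 195 − 38 = 157 to 223 − 36 = 187 |
| PFS assessment, 2 months from treatment start | about D62 | 62 − 38 = 24 to 62 − 36 = 26 |
| PFS assessment, 6 months from treatment start | about D184 | 184 − 38 = 146 to 184 − 36 = 148 |

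The calendar dates no MRI between baseline and D35. The off-study MRI has no fixed day and is done only if feasible.

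**Share of the PFS window.** Six months is 182.6 days, of which 34 pass before D35: (182.6 − 34) / 182.6 = 0.81.

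**Illustration for 6-month PFS (all inputs assumed).** Let S be 6-month PFS without later therapy, f the fraction starting therapy at D35, and HR its effect on the PFS hazard. With h = −ln(S)/182.6:

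reported PFS = exp(−34h) × [(1 − f) exp(−148.6h) + f exp(−148.6 × HR × h)]

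- S = 0.40, f = 0.50, HR = 0.7: h = 0.00502, and 0.843 × [0.5 × 0.474 + 0.5 × 0.593] = 0.450, a rise of 5 points.
- Over S = 0.30-0.50, f = 0.25-0.75 and HR = 0.5-0.9, the rise runs from 0.7 to 14.2 points.
- For scale, the binomial standard error at S = 0.40 with the 16 patients planned at the RP2D is √(0.4 × 0.6 / 16) = 0.122, about 12 points.

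**Marrow samples.** Week 8 is D50-D56, which is 50 − 38 = 12 to 56 − 36 = 20 days into new therapy. The first two-month follow-up, counted from the end of WBRT, is D80-D94, or 42 to 58 days in. Either lies after D35, but the sections do not agree on which applies. The calendar's blood-work row also ends at the DLT visit, so no blood count is scheduled to pair with the last granulocyte sample.

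**The case against.** Several points on the other side stand.

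- *The analyses are descriptive.* There is no comparator, test or go/no-go threshold on response or PFS, and 2.6.2 itself calls a valid survival analysis unlikely. This limits the weight of the point. It does not remove it, because a descriptive rate still misleads if readers cannot see how many patients were on another active treatment.
- *Counting progression or death regardless of later therapy is a coherent definition of PFS.* Agreed; it should stay. Censoring at new therapy can itself be informative.
- *The illustrated PFS shift is mostly within sampling error.* True at the mid-range (5 points against 12). But the shift would tend to go one way if the later therapy works, and it need not be equal across tumour groups.
- *Therapy started after intracranial progression does no harm here.* Correct: best response has stopped and the PFS event has occurred. Only therapy begun before intracranial progression matters.
- *Drugs are already captured under 5.3.* This makes the fix cheap, but no analysis is told to use the data, and that instruction covers drugs, not radiosurgery or surgery.

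A reader might also infer that new chemotherapy reverses the relation between %IUdR-DNA and blood counts. The documents do not support that. Section 2.6.3 expects no linear relation with counts; the hypothesis it will test relates dose and plasma pharmacokinetics to incorporation. Section 13.4.3 is descriptive, and it is unclear whether the last pair is collected at all.

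**Conclusion.** The point holds for best response and intracranial PFS. Under the stated rules, effects of systemic or intracranial local therapy begun after D35 and before intracranial progression are included in results presented as radiosensitization, and no scheduled MRI separates the two. For the marrow marker it holds only conditionally: any pair taken after new systemic therapy needs a flag, and the sampling schedule must be settled first.

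The size of the bias is unknown. The documents give no uptake or effect of later therapy, so the 1 to 14 point range is an assumption, not an estimate, and no figure for inflation of the response rate can be supported. A reader might infer that the recommended dose is compromised. It is not on this ground: under the D35 window, permitted systemic and intracranial local therapy starts only after the DLT assessment. The point concerns the interpretation of secondary and exploratory results, and is worth fixing because the remedy is small.

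**What to change.** - **Data.** Record the type and start date of the first post-D35 anticancer therapy, systemic or intracranial local.
- **13.4.1.** Report responses first documented before that therapy separately from those first documented after it. Give the number of patients who had started by each response scan, overall and by tumour group.
- **13.4.4.** Keep intracranial PFS as defined and say that it counts events regardless of later therapy. Add a sensitivity analysis censoring at the start of new therapy, noting that this may be informative. Name the start date as the censoring date: for an early starter the last scan beforehand is the baseline MRI, which would leave no follow-up.
- **13.4.3.** First reconcile the last granulocyte sample time (Week 8 in 1.3.1 and 2.6.3, first two-month follow-up in 9.2.2 and footnote f) with the absence of follow-up blood work in the calendar. Then flag or exclude any granulocyte/blood-count pair taken after new systemic therapy.

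The cost is a few sentences, a type and date entry for the first new therapy, and one schedule clarification, with no change to patient care. The downside is that few responses may be documented before new therapy. A patient who starts soon after D35 cannot contribute one from a scheduled scan, and a later starter can do so only if the site performs the recommended scans. Reporting those counts is still informative.
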